### Study Population

The RCT will include 24 moderately functioning, sedentary adults age 70 years or older with elevated levels of systemic inflammation but without overt disease conditions. We estimate that up to 324 potential participants will undergo screening procedures to identify 24 persons eligible for enrollment in the RCT.

Based on our previous studies, we anticipate that the average age of participants will be approximately 77.0 years, and that approximately 20% will be African Americans. In general, participants will have a relative low prevalence of comorbid diseases.

The key inclusion criteria are the following:

- (1) Age  $\geq 70$  years;
- (2) Mild to moderate physical impairment (Short Physical Performance Battery score  $\leq 10$ );
- (3) Sedentary lifestyle ( $< 120$  min per week of moderate intensity physical activity);
- (4) Chronic low-grade inflammation measured by IL-6  $> 2.5$  pg/ml. To minimize within person variability, IL-6 is the average of 2 measures taken 1-3 weeks apart at screening visits

See Table 1 for a complete list of eligibility criteria.

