### **In-Person Screening (Screening Visits 1 and 2)**

At Screening Visit 1, participants will be asked to give written informed consent for in-person screening tests and will then be evaluated for cardiovascular and other major diseases by a health review. The health review consists of a review of criteria in the telephone screen, medical and hospital admission history, medication inventory, and physical exam including blood pressure, pulse, weight, and waist circumference.

Short Physical Performance Battery (SPPB) will be performed and the Physical Activity Questionnaire will be administered.

Mini Mental Status Exam (MMSE) and Center for Epidemiological Studies – Depression Scale (CES-D) will be administered to identify potential participants with cognitive dysfunction or

clinically significant depression that would preclude participation. Participants will also provide a blood sample for additional eligibility requirements and participant safety measures.

Approximately 60 ml of blood will be drawn for laboratory tests to assure eligibility (complete metabolic panel, CBC with differential, serum ferritin, and IL-6).

Results of Screening Visit 1 will be reviewed by the PI or his designee. . At this time a copy of the Informed Consent document for the main study will be provided, to allow adequate opportunity for review and consideration before the baseline visit when consent for the main study is obtained. Ineligibles will be contacted by the Study Coordinator for an explanation of ineligibility and will receive a copy of abnormal laboratory results.

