### **Enrollment and Randomization**

24 eligible participants will be enrolled and randomized to allow for 6 participant failures or withdrawals

At the baseline visit, the Informed Consent document for the RCT will be reviewed with the potential participant and written consent obtained. Participants will undergo a battery of physical performance tests (400-meter walk; short physical performance battery, grip strength and endurance), formal tests of cognitive function, and a blood draw of about 60 ml (See Table 1). Quality of Life and pain will be assessed with the AM-PAC, the SF-36, and the Brief Pain Inventory (BPI). Self-report of physical activity and dietary fat intake will be obtained through brief questionnaires (RAPA and Block High Fat screen).

Participants will then be randomized to receive either curcumin (1000 mg/day; n = 15) or placebo (microcrystalline cellulose; n=15) for a three-month period. The study drug will be provided for the first month according to randomization.

Participants in both groups will be instructed to return to the research center every month for the duration of the three-month trial. At the monthly visits, compliance with the supplementation regimen for the previous month will be assessed by pill count and participants will be provided with another month's supply of study medication according to initial randomization. Participants will be queried about any adverse events they experienced since their previous visit and any medical history updates they may need to provide. Additionally, blood samples will be obtained (chemistry 15 panel and complete blood count) to ensure that no adverse changes have occurred since their previous visit.

To enhance retention and to ensure participant safety, participants will receive bi-weekly telephone calls throughout the intervention period to ascertain adverse events and express appreciation for participation.

Following the three month supplementation period (Month 3 visit), participants will complete a post-treatment assessment including the battery of physical performance tests (400-meter walk, short physical performance battery, grip strength and endurance); cognitive function tests; questionnaires for quality of life, pain symptoms, and physical activity; and a blood draw of approximately 60 ml (See Table 2).

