Approximately 3-4 weeks after the Month 3 visit (at Week 15 – 16), participants will receive a final telephone call to ascertain any late adverse events, discuss any abnormalities from the final safety lab results, and express appreciation for participation.

Table 2. Study Visit Schedule Visit Type	Phone screen (pre-screening)	Screening visit 1		Baseline visit	Week 2	1-Month Visit	Week 6	2-Month Visit	Week 10	3-Month visit	Week 15-16
	Basic eligibility screening	X	X								
Informed Consent (Screening)		X									
Health review and physical examination (including BP, pulse, weight, height, waist circumference)		X									
Medical History and Concomitant Medication		X									
Update Medical History and Concomitant Medication Info				X	X	X	X	X	X	X	
BP, pulse, height and weight, waist circumference		X		X	X	X	X	X	X	X	
MMSE, CES-D		X									
Physical Activity Questionnaire (RAPA)				X						X	
SPPB (including 4 m walk test)		X		X						X	
Phlebotomy		X		X	X	X	X	X	X	X	
IL-6		X								X	
Additional exploratory inflammatory markers (TBD)				X						X	
CBC and Comprehensive Metabolic Panel (CMP) (Safety blood tests)		X		X	X	X	X	X	X	X	
Informed Consent (Main Study), enrollment, and randomization				X							
400 m walk test				X						X	
Isokinetic dynamometry of knee flexors and extensors				X						X	
Isometric hand grip strength				X						X	
Cognitive Function Tests (NIH Toolbox)				X						X	
Quality of Life (AM-PAC, SF-36)				X						X	
Brief Pain Inventory				X						X	
Dietary Fat questionnaire (Block)				X							
Dispense study drug				X	X	X	X	X	X	X	
Scheduled phone call					X	X	X	X	X	X	X
Assess compliance, query adverse effects and events						X	X	X	X	X	X

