## **Outcome Measures**

### a. Physical Function Measures.

400-meter walk test will assess gait speed. Participants will be asked to walk at their usual pace, without over-exerting. They can stop for up to 1 min for fatigue or other symptoms. Participants will be allowed to use a cane, but not a walker, to complete this test. The results from this test are directly related to whole body aerobic capacity, which has been found to be strongly associated ( $r > 0.70$ ) with mitochondrial function in both younger and older adults.

Short physical performance battery (SPPB) will assess functional performance on different tasks including timed short distance walk, repeated chair stands and a balance test. The battery will be administered by a trained and certified examiner.

We will conduct additional tests of isolated muscle function by performing unilateral knee extension and flexion maximal strength and endurance testing. This test involves using an isokinetic dynamometer set at 90 degrees per second. Methods similar to that previously described by our group will be used. We have reported the reliability of strength testing to be very high (ICC=0.97; coefficient of variation=4.1%) when the testing sessions are separated by 4-weeks. Participants will perform 50 maximal knee extension and flexion concentric repetitions, which will be administered by trained and certified research assistants. Maximal muscle strength will be summarized as peak torque achieved in Newton-meters. A muscle endurance index will be calculated as the decline in peak torque over the 50 repetitions. This will be calculated as a slope and be used to evaluate the effect of curcumin on muscle endurance.

Grip strength will be measured with a hand-held dynamometer as the average of three readings

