e. Pain Assessments. The Brief Pain Inventory (BPI) will be used to assess the presence and location of daily pains, as well as pain severity and pain-related interference. The BPI measures pain severity using a series of 0 (no pain) to 10 (worst possible pain) scales, which assess average pain, worst pain, and least pain in the past week, as well as current pain at the time of testing. There are seven BPI interference questions, each ranging from 0 (does not interfere) to 10 (completely interferes), assessing the extent to which pain has interfered over the past 24 hours with general activity, mood, walking ability, normal work, relations with other people, sleep, and enjoyment of life. This instrument has been validated for assessing outcomes in participants with non-cancer pain and has been used to quantify treatment outcomes.

f. Systemic Inflammatory biomarkers. Standard inflammatory biomarkers (i.e., IL-6, TNFa, and novel markers of inflammation) will be measured by ELISA at Baseline and the 3-month visit. All samples will be measured in duplicate and the average of the two measures will be used for data analyses.

g. Other measures

Dietary Fat (Block) questionnaire. Poor absorption of curcumin has been reported for various preparations, with enhanced absorption in high fat diets. This brief (13 item) "fat screen" identifies individuals with "high" fat intake, a potential confounder due to enhanced curcumin absorption.

Self-reported physical activity. The Rapid Assessment of Physical Activity (RAPA) is a 9-item questionnaire developed to assess strength, flexibility, and level and intensity of physical activity among older adults.

Safety. As a safety check to ensure no adverse biological changes have occurred, the following measures will be completed at screening, baseline, and each monthly visit:

- Study Coordinator will review any changes in medication, ED visits or hospitalizations, or side effects since previous visit with the participant
- At monthly visits, 30 cc of blood will be drawn and analyzed for a CHEM-15 metabolic profile (Albumin, Albumin/Globulin Ratio (calculated), Alkaline Phosphatase, ALT, AST,

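### The plan does not settle which IL-6 sample is the baseline for its primary outcome: Table 2 points to the screening sample, the biomarker section to the Baseline visit

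*Combined protocol and SAP*

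**What the plan says.** Four places in the combined protocol and SAP bear on the baseline IL-6 value.

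- **Statistical Analyses** names the mean change in IL-6 as the primary outcome of the pilot. It defines every change as the 3-month value minus the baseline value, with 95% confidence intervals both within and between groups. It does not identify the baseline sample.
- **Table 2 (Study Visit Schedule)** marks IL-6 at Screening visit 1 and at the 3-month visit. In the Baseline column only the additional exploratory inflammatory markers are marked.
- **Outcome Measures, f. Systemic Inflammatory biomarkers** says that the markers, IL-6 included, "will be measured by ELISA at Baseline and the 3-month visit". It asks for duplicate measurement but has no rule on storage, batching or running paired samples together.
- **Study Population** and **In-Person Screening** use IL-6 as an entry test. The first says "IL-6 is the average of 2 measures taken 1-3 weeks apart at screening visits"; the second says "Approximately 60 ml of blood will be drawn for laboratory tests to assure eligibility".

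The visits also differ in content. At screening, "Short Physical Performance Battery (SPPB) will be performed". The 400 m walk, grip strength and the Table 2 item "Isokinetic dynamometry of knee flexors and extensors" are scheduled only at Baseline and 3 months. Blood is drawn at both of those visits: Enrollment and Randomization lists "formal tests of cognitive function, and a blood draw of about 60 ml" for Baseline and "questionnaires for quality of life, pain symptoms, and physical activity; and a blood draw of approximately 60 ml" for Month 3.

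**The concern.** A site or laboratory working from Table 2 would hold no IL-6 result from the Baseline visit, so the screening result would have to serve as baseline. That result is needed before enrollment. The Month 3 sample does not exist until about three months after randomization. Unless the screening sample is stored and re-assayed, which the plan does not mention, the two values almost certainly come from different assay runs. They also come from visits with different physical testing.

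Any systematic difference between runs or sampling conditions would then appear as a change in IL-6 within each arm. The plan reports those within-group changes with confidence intervals, and Specific Aims intends the pilot to supply effect sizes for later trials. Randomization does not protect a within-group change.

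**Working it through.** **1. The two schedules side by side.**

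| | Table 2 followed | Biomarker section followed |
|---|---|---|
| Baseline IL-6 sample | Screening | Baseline visit |
| Later sample | Month 3 | Month 3 |
| Physical tests at the earlier visit | SPPB only | 400 m walk, SPPB, grip, dynamometry |
| Physical tests at Month 3 | 400 m walk, SPPB, grip, dynamometry | The same |
| Same assay run? | Almost certainly not, because the result is needed for entry | Possible, but not required |

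Under the biomarker section the test battery is the same at both visits, so an average effect of it would largely cancel. A run difference could still remain. Under Table 2 neither cancels within a group.

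**2. The plan's own figure.** Inputs from Statistical Analyses: 15 per group, 20% attrition, SD 0.52 for log(IL-6), effect size 1.2, 80% power. Alpha is not stated; two-sided 0.05 is assumed.

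- Evaluable per group: 15 × 0.8 = 12.
- Two-sample t-test, n = 12 per group, effect size 1.2: power 0.802. The stated 80% is reproduced.
- Detectable difference: 1.2 × 0.52 = 0.624, given as 0.62. 1 − exp(−0.62) = 0.462, the stated 46%.

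The present point does not alter this figure.

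**3. Precision of a within-group change.** With SD 0.52 and n = 12, the 95% half-width is t(0.975, 11) × 0.52/√12 = 2.201 × 0.150 = 0.33 log units.

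**4. Effect of a shift between the two samples.** The documents give no size for a run or sampling-condition shift, so these sizes are assumptions. A multiplicative shift s moves the log change by ln(1 + s). Non-coverage is the chance that the nominal 95% interval misses the true within-group change, from the noncentral t distribution with 11 degrees of freedom.

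| Assumed shift | Move in log change | Share of half-width 0.33 | Share of detectable 0.62 | Non-coverage |
|---|---|---|---|---|
| 5% | 0.049 | 15% | 8% | 6% |
| 10% | 0.095 | 29% | 15% | 9% |
| 25% | 0.223 | 68% | 36% | 27% |
| 50% | 0.405 | 123% | 65% | 69% |

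**5. Effect on the between-group difference.** If both arms carry the same shift b, the expected difference is (curcumin change + b) − (placebo change + b), and b drops out.

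**The case against.** A reader might infer three stronger things, and the documents support none of them.

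*That blood is drawn after exercise at Baseline and Month 3, so IL-6 is raised by the tests.* The Physical Function section does say "Participants will perform 50 maximal knee extension and flexion concentric repetitions", and the draw is listed after the performance tests. But a list is not a sequence. The Baseline questionnaires follow the draw in the same text, and Table 2 lists phlebotomy above the walk and dynamometry. A draw before the tests fits the text equally well. The 400 m walk is done at usual pace. At screening the SPPB is described before the blood sample, so that sample is not documented as rested either. The documents do not discuss an acute rise in IL-6 after exertion; it would be an assumption.

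*That the treatment comparison is biased.* A shift common to both arms leaves its expectation unchanged. A biased contrast would need curcumin to improve effort enough to raise IL-6 in that arm, and nothing in the documents quantifies that chain.

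*That power is lost.* If individual responses with an assumed SD of 0.1, 0.2 or 0.3 are added, √(0.52² + s²) gives 0.53, 0.56 or 0.60, and power at 0.62 becomes 78%, 74% or 68%. Assumed between-run CVs of 5%, 10% or 15% at both time points give 79%, 77% or 73%. But 0.52 is an observed residual error from an earlier trial and may already contain such variation, so adding it again risks double counting. Error shared by all samples in a run is a common shift, not independent noise per participant.

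It is also fair to say that this is a pilot meant for descriptive estimates, and that the smallest assumed shifts matter little. What remains is the conflict over the baseline sample and its effect on the within-group changes.

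**Conclusion.** The point holds as a conflict over the baseline IL-6 sample. Table 2 and the biomarker section give different schedules for the primary outcome, and Statistical Analyses does not choose between them. If Table 2 is followed, the within-group changes are exposed to run and sampling-condition shifts: 0.10 log units for an assumed 10% shift and 0.22 for 25%, against a half-width of 0.33. The randomized between-group difference is protected in expectation as long as both arms are handled alike.

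The sizes rest on assumed shifts, on 12 evaluable participants per group, on an analysis on the log scale, and on 0.52 serving as the SD of the change. That 0.52 is a baseline-adjusted error, so the SD of the raw change may be larger and the half-width wider. That the screening and Month 3 assays fall in different runs is inferred from the entry requirement; the plan states no assay timing.

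**What to change.** - **Table 2:** mark IL-6 in the Baseline column.
- **Study Population and In-Person Screening:** state that screening IL-6 is used for eligibility only.
- **Systemic Inflammatory biomarkers:** state that each participant's stored Baseline and Month 3 samples are assayed in the same run.
- **Statistical Analyses:** name the Baseline-visit sample as the baseline, and make the between-group difference the main contrast, with within-group changes as description.
- **Enrollment and Randomization, as a precaution:** state that blood is drawn before the physical tests at both visits. This adds no procedure and removes the question of order; it does not correct a documented error.

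The cost is freezer storage and, relative to Table 2, one additional Baseline IL-6 assay per participant. Blood is already drawn at both visits, so there is no extra visit and no extra draw.

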### Dietary Supplement Intervention

Participants will be given identical capsules containing either: (1) curcumin (1000 mg/day), or (2) placebo (microcrystalline cellulose) and will be instructed to consume two 500 mg capsules prior to breakfast every morning with a glass of water. Participants will be instructed to follow this dosing regimen throughout the entire three-month treatment period. Compliance with the dosing regimen will be monitored both through interview and by counting capsules left at monthly clinic visits.

Curcumin – C3 Complex (Sabinsa Corporation, Piscataway NJ) will be used as the curcumin preparation. Each 500 mg capsule of C3 Complex contains 450 mg of curcumin, 40 mg of desmethoxycurcumin, and 10 mg of bisdemethoxycurcumin. Based on findings from recent studies demonstrating supplementation with curcumin reduced systemic inflammation in middle-age adults, the selected dose will be 1000 milligrams per day in 2 divided doses. In safety studies, this dosage level has been determined to be safe for human consumption.

Placebo – Participants will consume microcrystalline cellulose in capsules identical to C3 Complex. There are no active ingredients in the placebo capsules.

## **Outcome Measures**

### a. Physical Function Measures.

400-meter walk test will assess gait speed. Participants will be asked to walk at their usual pace, without over-exerting. They can stop for up to 1 min for fatigue or other symptoms. Participants will be allowed to use a cane, but not a walker, to complete this test. The results from this test are directly related to whole body aerobic capacity, which has been found to be strongly associated ( $r > 0.70$ ) with mitochondrial function in both younger and older adults.

Short physical performance battery (SPPB) will assess functional performance on different tasks including timed short distance walk, repeated chair stands and a balance test. The battery will be administered by a trained and certified examiner.

We will conduct additional tests of isolated muscle function by performing unilateral knee extension and flexion maximal strength and endurance testing. This test involves using an isokinetic dynamometer set at 90 degrees per second. Methods similar to that previously described by our group will be used. We have reported the reliability of strength testing to be very high (ICC=0.97; coefficient of variation=4.1%) when the testing sessions are separated by 4-weeks. Participants will perform 50 maximal knee extension and flexion concentric repetitions, which will be administered by trained and certified research assistants. Maximal muscle strength will be summarized as peak torque achieved in Newton-meters. A muscle endurance index will be calculated as the decline in peak torque over the 50 repetitions. This will be calculated as a slope and be used to evaluate the effect of curcumin on muscle endurance.

Grip strength will be measured with a hand-held dynamometer as the average of three readings

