### Specific Aims:

Specific Aim 1 - To examine the effects of dietary supplementation with curcumin on changes in physical function (walking speed, muscle fatigue, and grip strength) and in

self-reported physical activity

*Hypothesis 1 – Dietary supplementation with curcumin will maintain or improve walking speed, muscle fatigue, strength, and physical activity compared to controls.*

*Specific Aim 2 – To examine the effects of dietary supplementation with curcumin on cognitive performance (attention, memory), and pain symptoms.*

*Hypothesis 2 - Dietary supplementation with curcumin will maintain or improve attention and memory and reduce pain symptoms.*

*Specific Aim 3 – To examine the effects of dietary supplementation with curcumin on markers of systemic inflammation*

*Hypothesis 3 - Dietary supplementation with curcumin will decrease levels of IL-6 and of other systemic and cellular biomarkers of inflammation*

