## **Statistical Analyses**

Sample size estimates for pilot studies are inherently difficult because by intent, a pilot study is meant to include a smaller sample than a fully powered study. The enrollment sample of 15 participants in the intervention group and 15 participants in the placebo group (allowing for at least 12 evaluable participants in each group after the expected 20% loss due to attrition) is intended to provide sufficient data to indicate feasibility of a larger study and to provide descriptive estimates of effects. Additionally, it will provide for nominal estimation (using a 95% confidence interval) of the mean changes in the inflammatory marker, IL-6, the primary outcome of this pilot.

Feasibility and acceptability of the proposed intervention in older adults will be evaluated by process variables including number of participants completing the study; medication compliance, number and severity of adverse events, and changes in Quality of Life attributable to study participation.

Efficacy will be assessed as effects of the intervention on functional performance (physical and cognitive measures; pain perception, and inflammatory processes (Specific Aims). The following outcomes will be evaluated: physical function (walking speed, muscle fatigue); cognitive function (attention, executive, and memory function); pain (self-report); and systemic inflammation (IL-6, CRP, TNF $\alpha$ , and novel markers)

For each outcome, we will take the value of that outcome after the 3-month supplementation period minus the value at baseline for each participant. Summary statistics and 95% confidence intervals will be provided for within group changes as well as between group differences.

Effect size of intervention on key outcomes for sample size calculations in the planning of a larger RCT. Based on a sample size of 15 per group and 20% attrition, we have 80% power to detect a between group difference of effect size 1.2. Specifically, if we use the root mean squared error from LIFE-P (adjusted for baseline log(IL-6) and treatment) of 0.52 for log(IL-6), then we can detect a mean difference of 0.62 (on the log scale) or equivalently the difference between 4.20 and 2.26 pg/ml (or a 46% difference). And for selection based on walking speed change, we used a within group standard deviation of 0.25, which leads to a detectable mean difference of 0.3 m/s.

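### The muscle endurance index is stated as an unnormalised torque slope, so a between-arm difference in knee strength change would be read as a difference in fatigability

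*Combined protocol and SAP*

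**What the plan says.** In the protocol, section 6, Outcome Measures, part a (Physical Function Measures), the knee test is an isokinetic protocol: "Participants will perform 50 maximal knee extension and flexion concentric repetitions". Two summaries come from it. For strength, "Maximal muscle strength will be summarized as peak torque achieved in Newton-meters". For endurance, "A muscle endurance index will be calculated as the decline in peak torque over the 50 repetitions", followed by "This will be calculated as a slope and be used to evaluate the effect of curcumin on muscle endurance". No reference torque, unit or sign is given for the endurance index. The same paragraph says "Methods similar to that previously described by our group will be used" and cites earlier work.

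Hypothesis 1 in section 5 is that curcumin "will maintain or improve walking speed, muscle fatigue, strength, and physical activity compared to controls". Statistical Analyses lists "physical function (walking speed, muscle fatigue" among the efficacy outcomes. It analyses every outcome as the month 3 value minus the baseline value, with 95% confidence intervals within and between groups, and states no adjustment for change in strength. The documents do not say outright that the endurance index is the muscle fatigue outcome, but no other measure in them fits that name.

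**The concern.** A slope of torque on repetition number carries two things: how strong the participant is at the start, and what share of that strength is lost. Only the second is fatigability in the usual relative sense. Someone who becomes stronger and still loses the same percentage over 50 repetitions has a steeper slope, and would be recorded as fatiguing more. Someone who becomes weaker would be recorded as fatiguing less.

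The trial tests a product that might affect strength, and the index is analysed as a change score compared between arms. Any difference between arms in knee-torque change would therefore pass straight into the fatigue result. Overall objective 3 is to obtain effect sizes for sizing future trials, so a mixed index could hand the next trial a wrong input.

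**Working it through.** **The plan's own figure.** The documents give no numerical target for the endurance index. The nearest figure is general: 15 per group with 20% attrition leaves 15 × 0.80 = 12 per group, with 80% power at a standardised difference of 1.2. A two-sample t-test with 12 per group, two-sided 0.05, gives power 0.802, so that figure reproduces. It is used below only for the group size and as a yardstick.

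**Proportionality (needs no assumed size).** Write torque at repetition k as T0 × h(k), where h is the relative fatigue curve. The fitted slope is T0 × b, where b is the slope of h. If starting torque becomes T0 × (1 + g) and h is unchanged, the slope becomes T0 × (1 + g) × b, which is steeper by exactly the fraction g. This was confirmed for starting torques of 60, 80 and 100 Nm, total declines of 30%, 40% and 50%, linear and exponential curves, and gains of 5%, 10% and 20%.

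Example (assumed values: linear fall of 40%, 49 intervals between 50 repetitions):
- From 100 Nm: 40/49 = 0.816 Nm lost per repetition.
- From 110 Nm: 44/49 = 0.898 Nm lost per repetition, 10% steeper.
- Relative to own starting torque: 40%/49 = 0.816% per repetition in both cases.

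**Masking.** With a strength gain g, the raw slope shows no change when the true relative decline has improved by g/(1 + g). For g = 10% that is 0.10/1.10 = 9.1%. An improvement smaller than this would appear as worsening.

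**Size in standard deviation units.** This needs quantities that the documents do not give. Inputs:
- 12 evaluable per arm (Statistical Analyses).
- Torque variation of 4.1% per test (the protocol's coefficient of variation for strength testing, reported for sessions 4 weeks apart; it is not a figure for slopes).
- Assumed: mean decline 0.40, starting torque SD 25% of its mean, within-person SD of fractional fatigue s per visit, and strength gain g in the curcumin arm only.

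The SD of the slope change, as a share of the mean slope, is approximately √2 × √(0.041² + (s/0.40)²) × √(1 + 0.25²), and the spurious standardised effect is about -g divided by that.
- s = 0.03: √2 × √(0.00168 + 0.00563) × 1.031 = 0.125; -0.10/0.125 = -0.80.
- s = 0.10: √2 × √(0.00168 + 0.0625) × 1.031 = 0.369; -0.10/0.369 = -0.27.

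Simulation of the same design (20,000 trials per setting), 10% gain, no change in relative fatigability:

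| Assumed s | Spurious effect (SD units) | 95% CI excludes zero, wrong direction |
|---|---|---|
| 0.03 | about -0.8 | 43% to 45% |
| 0.05 | about -0.5 | 22% |
| 0.08 | -0.33 | 12% |
| 0.10 | -0.26 | 9% |

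With a 5% gain the effect runs from about -0.4 (15%) at s = 0.03 to -0.13 (5%) at s = 0.10. The rate expected by chance in one direction is 2.5%, and the relative index gave about 2.5% each way throughout. With g = 0 the shift is zero.

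**The case against.** Five objections deserve weight.

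- **The unit is inferred.** Newton-meters is attached to the strength summary, not to the endurance index, and the cited methods may contain a normalisation. This stands as a limit on certainty. But the plan spells out this index itself and states no normalisation, and a treatment outcome should not depend on one the reader cannot see.
- **The bias is conditional.** A reader might infer that the index is bound to work against curcumin. The documents do not support that. Hypothesis 1 allows strength to be maintained as well as improved, and equal change in both arms from similar baselines, through practice for example, produces no between-group bias. The distortion needs a difference between arms in knee-torque change. It can also arise because strength is better preserved on curcumin, and it would favour curcumin if curcumin lowered strength.
- **The hypotheses do not conflict by construction.** A reader might infer that the strength and fatigue parts of Hypothesis 1 oppose each other. Specific Aim 1 names grip strength, measured on a separate hand-held device, which does not enter the knee slope. The coupling is with knee torque only.
- **Fatigue could mean absolute torque loss.** On that definition the steeper slope is the right answer. If that is the intention, the plan should say so; it does not.
- **The stakes are limited.** IL-6 is the primary outcome, the trial is a pilot reporting estimates with intervals, and peak torque comes from the same test, so a strength-driven slope change could be seen and recalculated. This lowers the priority. It does not make the index a clean measure of fatigability.

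**Conclusion.** The concern holds in conditional form. On the plain reading, the endurance index scales one for one with starting knee torque, and the planned change-score comparison has nothing to separate strength from fatigability. That much follows from the formula alone and rests on no assumed values.

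Whether this misleads depends on knee torque changing differently between arms, which the documents neither establish nor rule out. The size cannot be set from them either. For an assumed 10% gain on curcumin it is about -0.25 to -0.8 SD, with a wrong-direction interval in roughly 9% to 45% of trials as the assumed within-person SD of fractional fatigue goes from 0.10 to 0.03. Quoting only the upper part of that range would overstate what is known. All of these effects are smaller than the 1.2 SD difference the trial is powered to detect, but they would matter if carried into the planning of a larger trial. This is a cheap improvement to a non-primary outcome.

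**What to change.** Replace the definition with one relative to the participant's own torque at the same visit: either the percentage decline from the mean of the first few repetitions, or the slope of log peak torque on repetition number. The log version works because multiplying all torques by 1 + g adds a constant on the log scale and leaves the slope unchanged. State the unit and which direction means more fatigue. Report absolute peak torque separately as the strength result. If the cited methods already normalise the slope, write that rule into the protocol.

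The cost is about one sentence and a different formula. No new data are needed as long as torque is kept for each repetition, which the planned slope already requires. The downside is a little extra noise from the reference torque, which averaging several early repetitions limits; the simulation above did not include that noise.
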